2.1 Study Treatment Discontinuation

Subjects may discontinue study treatment or withdraw their consent to participate in the study at any time without prejudice. The Investigator may withdraw a subject from study treatment or from the study if, in his or her clinical judgment, it is in the best interest of the subject or if the subject cannot comply with the protocol.

In addition, any of the following conditions requires discontinuation of the subject from study treatment:

- An AE or intercurrent illness that in the opinion of the Investigator warrants the subject's withdrawal from study treatment.
- The Investigator believes it is not in the best interest of the subject to continue on study.
- Specific conditions described in the Management of Adverse Events Section 5.4.
- Necessity for treatment with other anticancer treatment prohibited by protocol.
- Sexually active subjects who refuse to use medically accepted barrier methods of contraception
 (e.g., male condom, female condom) during the study and for 4 months after the last dose of
 cabozantinib and 3 months after the last dose of ipilimumab and 5 months after the last dose of
 nivolumab.
- Women who become pregnant or are breastfeeding.
- If the subject does not recover from his or her toxicities to tolerable Grade ≤ 2 within 6 weeks,
 the subject will have study treatment discontinued unless there is unequivocal evidence that the
 subject is benefitting. In this situation, a subject may be able to restart therapy with a dose
 reduction upon resolution of the toxicity and with agreement of the Principal Investigator.
- Necessity for interrupting all study treatment for greater than 12 weeks for study-treatmentrelated AEs unless approved by the Principal Investigator.

- Request by regulatory agencies for termination of treatment of an individual subject or all subjects under the protocol.
- Significant noncompliance with the protocol schedule in the opinion of the Investigator.
- Subjects who cannot tolerate the minimum protocol-specified dose of study treatment will have study treatment discontinued.
- Progressive disease (PD) or the subject no longer experiences clinical benefit as determined by the Investigator. Patients who continue study treatment beyond progression must be reconsented into the study.
- Subject participation in another clinical study using an investigational agent, investigational medical device, or other intervention.

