5.4.2 Management of AEs Associated with Nivolumab and Ipililumab

The assigned dose for Nivolumab 3 mg/kg IV every 3 weeks followed by 480mg every 4 weeks.

The assigned dose for Ipilimumab 1 mg/kg for a maximum of up to 4 doses.

Dose reductions are not allowed for the IO agents. AEs associated with the IO agents are managed with dose delays.

For more detailed guidance on management of non-hepatocellular AEs associated with IO agents please see Appendix A. For recommendations on management of hepatocellular toxicity and dose modifications of both cabozantinib and IO agents, see Section 5.4.3.

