5.4.2.1 Dose Delay Criteria for the Nivolumab and Ipililumab

Administration of the Nivolumab and Ipililumab should be delayed, for any of the following:

- Any Grade 2 non-skin, drug-related AE, with the exception of fatigue
- Grade 2 drug-related creatinine, AST, ALT, and/or total bilirubin abnormalities
- Any Grade 3 skin, drug-related AE
- Any Grade 3 drug-related laboratory abnormality, with the following exceptions:
 - Grade 3 lymphopenia does not require dose delay
 - Grade 3 amylase or lipase abnormalities that are not associated with symptoms or clinical manifestations of pancreatitis do not require a dose delay.
 - Grade 3 AST, ALT or total bilirubin may require dose discontinuation. (See Section 5.4.3)
- Grade 4 amylase or lipase value necessitates dose delay for the anti-PD-(L)1 and anti-CTLA-4 and
 abdominal imaging to rule out pancreatitis regardless of presence or absence of symptoms. If the
 diagnostic radiology scan shows no evidence of pancreatitis, the anti-PD-(L)1 and anti-CTLA-4 may
 CONFIDENTIAL Cabozantinib + Nivolimab + Ipililumab Protocol Required Elements

be resumed once the amylase and lipase values return to Grade 3 or lower as long as the subject remains asymptomatic.

 Any AE, laboratory abnormality, or intercurrent illness which, in the judgment of the Investigator, warrants delaying the dose of study medication.

Immuno-oncology agents are associated with AEs that differ in severity and duration from AEs caused by other therapeutic classes. Early recognition and management of AEs associated with immuno-oncology agents may mitigate severe toxicity. Management algorithms or tables (Section 5.4.3 and Appendix A) have been developed to assist investigators in assessing and managing the following groups of AEs:

- Gastrointestinal
- Renal
- Pulmonary
- Hepatic
- Endocrinopathy
- Skin
- Neurological
- Myocarditis
- Infusion-related Reactions

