5.4.2.2 Criteria to Resume Nivolumab and Ipililumab

Delayed doses of Nivolumab and Ipililumab should be administered as soon as the subject meets criteria to resume treatment. If a dose has been delayed, the subject should not wait until the next scheduled dosing date.

Subjects may resume treatment with these study drugs when the drug-related AE(s) resolve to Grade \leq 1 or baseline value, with the following exceptions:

- Subjects may resume treatment in the presence of Grade 2 fatigue.
- Subjects who have not experienced a Grade 3 drug-related skin AE may resume treatment in the presence of Grade 2 skin toxicity.
- Systemic corticosteroids for control of infusion reactions or irAEs must have been tapered to a dose level ≤ 10 mg/day of prednisone equivalent before resuming treatment with Nivolumab and Ipililumab.

- For subjects with AST, ALT, and/or total bilirubin abnormalities, dosing may resume when laboratory values return to baseline grade and corticosteroid therapy has been tapered to no higher than the equivalent of 10 mg of prednisone per day.
 - Note: Drug-related ALT or AST > 3x ULN in combination with total bilirubin > 2x ULN without reasonable other explanation, consistent with DILI mandates permanent discontinuation of all study drugs.

Note: Nivolumab and Ipililumab, or Ipililumab alone, may be continued after a Grade 3 ALT or AST has been observed and managed appropriately after a positive benefit risk ratio has been determined and the Principal Investigator has been consulted (See Section 5.4.3)

- Drug-related pulmonary toxicity, diarrhea, or colitis must have resolved to baseline before
 treatment is resumed. Subjects with persistent Grade 1 pneumonitis after completion of a steroid
 taper over at least 1 month may be eligible for retreatment if discussed with and approved by the
 Principal Investigator.
- Drug-related endocrinopathies adequately controlled with only physiologic hormone replacement may resume treatment.
- If all study treatment is interrupted for > 12 weeks, the subject must be permanently discontinued from study treatment unless approved by the Principal Investigator.

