5.4.2.3 Criteria for Discontinuation of Nivolumab and Ipililumab

Criteria for discontinuation of both Nivolumab and Ipililumab during the combination therapy period or the Nivolumab alone after no additional Ipililumab is to be given are specified in this section. If a subject meets criteria for discontinuation and the Investigator is unable to determine whether the event is related to both or one study drug, the subject should discontinue both Nivolumab and Ipililumab with the exception of certain cases of liver function test elevation (See Section 5.4.3).

Nivolumab and Ipililumab should both permanently discontinued for any of the following reasons:

- Any Grade 2 drug-related uveitis, eye pain or blurred vision that does not respond to topical therapy and does not improve to Grade 1 severity within the re-treatment period OR requires systemic treatment;
- Grade 3 drug-related uveitis, pneumonitis, bronchospasm, neurologic toxicity, myocarditis, hypersensitivity reaction, or infusion reaction of any duration;
- Any Grade 3 adrenal insufficiency regardless of control with hormone replacement.
- Any Grade 3 drug-related non-skin AE lasting > 7 days or recurs;
- Grade 3 diarrhea or Grade 3 colitis

- Note: Nivolumab alone can be continued if grade 3 colitis or diarrhea lasts ≤ 7 days or if, upon permanent discontinuation of ipililumab, the Principal Investigator approves continued use due to a possible favorable benefit/risk ratio.
- Grade 3 drug-related thrombocytopenia > 7 days or associated with bleeding;
- Grade ≥ 3 drug-related AST**, ALT**, or total bilirubin;
 - ** In most cases of Grade 3 AST or ALT elevation, Nivolumab and Ipililumab will be permanently discontinued. Nivolimab alone or Nivolumab and Ipililumab may be continued with approval from the Principal Investigator if there is a possible favorable benefit/risk ratio.
- Drug-related ALT or AST > 3x ULN in combination with total bilirubin > 2x ULN without reasonable other explanation, indicative of potential DILI, mandates permanent discontinuation of all study drugs;
- Grade 4 drug-related AE or laboratory abnormality (including but not limited to creatinine, AST, ALT, or total bilirubin);
- Any grade meningoencephalitis, myasthenia gravis, or Guillain-Barré syndrome
- Any event that leads to delay in dosing lasting > 12 weeks from the previous dose.

The following scenarios do not require discontinuation of the ipililumab and/or nivolumab:

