Rule out non-inflammatory causes. If non-inflammatory cause, treat accordingly and continue I-O therapy. Evaluate with imaging and pulmonary consultation.

Patients on IV steroids may be switched to an equivalent dose of oral corticosteroids (e.g. prednisone) at start of tapering or earlier, once sustained clinic improvement is observed. Lower bioavailability of oral corticosteroids should be taken into account when switching to the equivalent dose of oral corticosteroids

Endocrinopathy Adverse Event Management Algorithm

[figure not shown]
Rule out non-inflammatory causes. If non-inflammatory cause, treat accordingly and continue I-O therapy. Consider visual field testin endocrinology consultation, and imaging.

Patients on IV steroids may be switched to an equivalent dose of oral corticosteroids (e.g. prednisone) at start of tapering or earlier, once sustained clinical improvement is observed. Lower bioavailability of oral corticosteroids should be taken into account when switching to the equivalent dose of oral corticosteroids.

Skin Adverse Event Management Algorithm

Rule out non-inflammatory causes. If non-inflammatory cause, treat accordingly and continue I-O therapy.

Patients on IV steroids may be switched to an equivalent dose of oral corticosteroids (e.g. prednisone) at start of tapering or earlier, once sustained clinical improvement is observed. Lower bioavailability of oral corticosteroids should be taken into account when switching to the equivalent dose of oral corticosteroids.

[figure not shown]
^If SJS/TEN is suspected, withhold I-O therapy and refer patient for specialized care for assessment and treatment. If SJS or TEN is diagnosed, permanently discontinue I-O therapy.

CONFIDENTIAL - Cabozantinib + Nivolimab + Ipililumab Protocol Required Elements

^{*}Refer to NCI CTCAE v4 for term-specific grading criteria.

Neurological Adverse Event Management Algorithm

[figure not shown]
Rule out non-inflammatory causes. If non-inflammatory cause, treat accordingly and continue I-O therapy.

Patients on IV steroids may be switched to an equivalent dose of oral corticosteroids (e.g. prednisone) at start of tapering or earlier, once sustained clinical improvement is observed. Lower bioavailability of oral corticosteroids should be taken into account when switching to the equivalent dose of oral corticosteroids.

CONFIDENTIAL - Cabozantinib + Nivolimab + Ipililumab Protocol Required Elements

Myocarditis Adverse Event Management Algorithm

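### SJS and TEN are missing from the Section 5.4.2.3 permanent-stop list, so a diagnosed case below Grade 4 can be delayed and resumed under Section 5.4.2 but must stop for good under Appendix A

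*Combined protocol and SAP*

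**What the plan says.** Four places in the combined protocol and SAP govern this case.

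- **Section 5.4.2.1 (delay).** Among the reasons to delay nivolumab and ipilimumab is "Any Grade 3 skin, drug-related AE". At Grade 2, the general delay rule covers only non-skin events.
- **Section 5.4.2.2 (resume).** "Subjects may resume treatment with these study drugs when the drug-related AE(s) resolve to Grade" 1 or lower, or baseline. Systemic steroids must first be down to 10 mg/day prednisone equivalent or less. A skin exception adds: "Subjects who have not experienced a Grade 3 drug-related skin AE may resume treatment in the presence of Grade 2 skin toxicity". The section also says that a delayed dose should be given once the criteria are met, without waiting for the next scheduled date.
- **Section 5.4.2.3 (permanent stop).** The opening sentence says that criteria for stopping both agents, or "the Nivolumab alone after no additional Ipililumab is to be given are specified in this section". The general Grade 3 bullet reads "Any Grade 3 drug-related non-skin AE lasting > 7 days or recurs".
- **Appendix A, skin algorithm text.** IO therapy is withheld while SJS or TEN is suspected; after that, "If SJS or TEN is diagnosed, permanently discontinue I-O therapy".

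The texts are linked. Section 5.4.2 says: "For more detailed guidance on management of non-hepatocellular AEs associated with IO agents please see Appendix A". Section 5.4.2.1 lists skin among the event groups that have a management algorithm. Appendix A, however, introduces itself as general guidance to the Investigator. No sentence says which text governs if they differ.

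**The concern.** Appendix A treats a confirmed diagnosis of SJS or TEN as reason enough to end IO therapy. Section 5.4.2.3 can already stop by diagnosis: one bullet does so at any grade for meningoencephalitis, myasthenia gravis and one other neurological syndrome. SJS and TEN have no matching bullet, and the general Grade 3 rule that might have caught them leaves out skin events.

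Take a patient whose diagnosed Grade 3 SJS has settled to Grade 1, with steroids at 10 mg/day or less. An investigator working from Sections 5.4.2.1 to 5.4.2.3 may resume nivolumab and ipilimumab. One working from Appendix A may not. What is at stake is the safety of that patient, because the permanent stop then depends on which page is read, or on individual judgment. The endpoints, sample size and analysis are not affected.

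**Working it through.** No arithmetic beyond counting applies, and the plan gives no figure to reproduce. The check compares the rules.

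**Step 1: count the stop list.** Section 5.4.2.3 has 11 permanent-stop bullets, not counting sub-notes. Bullets naming SJS or TEN: 0 of 11. Bullets that stop by diagnosis at any grade: 1 of 11.

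**Step 2: find bullets that could catch SJS or TEN without naming them.** There are three:

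- the Grade 4 drug-related event bullet;
- the named Grade 3 list, if the event is classed as a hypersensitivity reaction;
- the bullet for delays of more than 12 weeks. The same section lists delays for prolonged steroid tapers among situations that do not require a stop, so this backstop may not be absolute. The point does not rely on that.

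**Step 3: compare outcomes for a diagnosed, drug-related SJS or TEN.**

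| Case | Sections 5.4.2.1–5.4.2.3 | Appendix A | Agree? |
|---|---|---|---|
| Grade 4 | Permanent stop | Permanent stop | Yes |
| Grade 3, classed as hypersensitivity reaction | Permanent stop, any duration | Permanent stop | Yes |
| Grade 3 skin event, delay over 12 weeks | Permanent stop (taper exception aside) | Permanent stop | Yes |
| Grade 3 skin event, delay of 12 weeks or less | Delay; may resume at Grade 1 or lower, or baseline | Permanent stop | **No** |
| Grade 2 skin event, if such a grade is assigned | No grade-based delay or stop; Investigator may delay | Permanent stop | **No** |

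**Step 4: check whether the skin exception closes the gap.** It does not. It withholds resumption at Grade 2 from patients who have had a Grade 3 skin event. Those patients stay under the general rule, so the section foresees their resuming at Grade 1 or lower.

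**Step 5: look for the same pattern elsewhere in Appendix A.** Three other permanent-stop triggers are not named in Section 5.4.2.3. Each conflicts only under conditions:

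- Grade 2 CRS not improved at 24 hours: depends on how the ASTCT grade used for management maps to CTCAE, which is not given, and on a later line in the same row that allows the next dose after symptoms resolve.
- Grade 3 CRS: conflicts only if it lasts 7 days or less, does not recur, and is not classed as an infusion or hypersensitivity reaction.
- Suspected HLH or MAS: conflicts only below Grade 4 and outside the 7-day or recurrence rule.

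**The case against.** The best defence is that the texts can be followed in sequence: hold a Grade 3 skin event, then stop once SJS or TEN is diagnosed. Section 5.4.2.2 gives permission to resume, so an investigator who stops for good breaches nothing. The body refers to Appendix A, and Section 5.4.2.1 names skin beside its reference to the algorithms. Section 2.1 also requires a stop for "An AE or intercurrent illness that in the opinion of the Investigator warrants" withdrawal from study treatment. A careful investigator would apply the stricter rule.

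Much of this stands, and it lowers the practical risk. It does not remove the inconsistency. The appendix presents itself as guidance, the resume rule covers the same patient, and Section 2.1 rests on opinion and does not make the stop mandatory for this diagnosis.

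Four stronger readings are tempting, and the documents do not support them:

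- *The plan orders re-treatment after SJS.* It permits resumption. The line about giving delayed doses promptly applies to subjects who meet the resume criteria; it does not override a stop.
- *The conflict holds for every diagnosed case.* It depends on the grade and on the event being handled as a skin event. The documents give no CTCAE grades for SJS or TEN, and classing the event as a hypersensitivity reaction would make Grade 3 a stop. Skin handling is the natural reading because the protocol puts SJS in the skin algorithm, but it remains an assumption.
- *The protective rule appears only in a footnote.* The skin algorithm figure is not shown in the text available, so what its boxes say cannot be checked.
- *CRS and HLH/MAS are contradictions of the same standing.* They depend on the grade mapping, duration and classification conditions set out above.

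**Conclusion.** The point holds in a narrow form. Section 5.4.2.3 names SJS or TEN in 0 of 11 bullets and excludes skin events from its general Grade 3 stop. The conflict with Appendix A arises if the diagnosed event is drug-related, is graded below 4, is handled as a skin event, and involves a delay of 12 weeks or less. Under those assumptions one text permits resumption and the other requires a permanent stop, with no statement of precedence. The documents give no event frequency, so the number of patients affected cannot be estimated.

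This should be corrected because it concerns a permanent-stop safety rule and the correction is simple. The CRS and HLH/MAS mismatches are secondary. The skin algorithm's reference to CTCAE v4, where Section 7.1.1 sets v5.0, is editorial.

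**What to change.** Make three wording changes:

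1. Add a bullet to the Section 5.4.2.3 stop list: *Diagnosed SJS or TEN, any grade.*
2. In Sections 5.4.2.1 and 5.4.2.2, except diagnosed SJS or TEN from the Grade 3 skin delay and resume rules.
3. State that where Appendix A calls for permanent IO discontinuation, including for CRS and suspected HLH or MAS, the stricter rule prevails and the event is not eligible for resumption.

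Two editorial changes can go in at the same time: say in the Grade 2 CRS row that the next-dose line applies only to patients who improved within 24 hours, and update CTCAE v4 to v5.0 in the skin algorithm note.

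The cost is protocol text, approved through the amendment route in Section 11. Visits, sample size and analysis do not change.
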